6.14. Subgroup Analyses

Subgroup analyses of the treatment interaction for important factors, including age group, race, gender, country, duration of diabetes ($<$ median, \geq median), baseline HbA1c ($< 8\%$, $\geq 8\%$), and BMI ($<$ median, \geq median), may be conducted for the primary endpoint of HbA1c. Country will use the pooled country.

These will be conducted using the MMRM with treatment, visit, subgroup, treatment-by-visit, treatment-by-subgroup, visit-by-subgroup, and treatment-by-visit-by-subgroup as fixed effects, and baseline as a covariate. If the MMRM fails to converge, the corresponding analysis of covariance (ANCOVA) or ANOVA model (LOCF) will be used.

When analyzing baseline HbA1c as a subgroup, the baseline HbA1c will not be included as a covariate to avoid colinearity.

TEAE exceeding 5% will be summarized descriptively for the patients with the top quartile of the body weight reduction from baseline by treatment group.

Other exploratory subgroup analyses may be performed as deemed appropriate.

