### 6.1. Inclusion Criteria

Patients are eligible to be included in the study only if they meet all of the following criteria at study entry (Visit 1), or at other visits, only when indicated:

- [1] are men or nonpregnant women aged  $\geq 18$  years;
- [2] have had T2D for  $\geq 6$  months according to the World Health Organization (WHO) classification ([Appendix 5](#));
- [3] have HbA1c of 7.0% to 10.0%, inclusive, as assessed by the central laboratory;
- [4] have been treated with stable doses of metformin for at least 3 months prior to Visit 1 and between Visit 1 and Visit 3; the metformin dose will be considered stable for this period if all prescribed daily doses were in the range between the minimum required dose ( $\geq 1500$  mg/day) and the maximum approved dose per country-specific label; lower doses will be allowed only with documented GI intolerability in the required dose range;
- [5] have had stable body weight for at least 3 months prior to Visit 1; body weight will be considered stable if it has not changed more than 5% in the past 3 months;
- [6] agree not to initiate a diet and/or exercise program during the study with the intent of reducing body weight other than the lifestyle and dietary measures for diabetes treatment;
- [7] have a body mass index (BMI)  $\geq 25$  kg/m^2;
- [8] in the investigator's opinion, are well-motivated, capable, and willing to:
  - [a] self-inject treatment as required for this protocol or come into the clinic for injections, up to 3 injections per week on the same day and within 30 minutes (visually impaired persons who are not able to perform the injections must have the assistance of a sighted individual trained to inject the study drug; persons with physical limitations who are not able to perform the injections must have the assistance of an individual trained to inject the study drug);
  - [b] perform fingerstick PG monitoring at least once daily and up to 6 times per day once weekly (per Schedule of Activities [[Section 2](#)]) throughout the trial;
  - [c] maintain a study diary as required for this protocol;

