#### **10.3.6. Subgroup Analyses**

Subgroup analyses of treatment interaction for important factors, including age, race, gender, country, duration of diabetes, baseline HbA1c (<8%, ≥8%), and BMI may be conducted for the primary endpoint of HbA1c.

These will be conducted using the MMRM with treatment, visit, subgroup, treatment-by-visit, treatment-by-subgroup, visit-by-subgroup, and treatment-by-visit-by-subgroup as fixed effects, and baseline as covariate. If the MMRM fails to converge, the corresponding analysis of covariance (ANCOVA) or ANOVA model (LOCF) will be used.

When analyzing baseline HbA1c as a subgroup, the baseline HbA1c will not be included as a covariate to avoid colinearity.

Other exploratory subgroup analyses may be performed as deemed appropriate.

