5.2. Determination of Sample Size

Assuming a screen failure rate of 30%, approximately 429 patients will need to be screened to attain approximately 300 patients randomized to the 4 treatment arms in a 1:1:1:1 ratio for 4.5 mg, 3.0 mg, 1.5 mg dulaglutide, or placebo weekly (~75 patients per arm). For the investigational dulaglutide dose arms (4.5 mg and 3.0 mg), approximately 38 patients will be assigned to each titration algorithm (Algorithms 1 and 2). Assuming a 20% dropout, this will result in approximately 60 patients per arm and 30 patients per algorithm (in each of the investigational-dose dulaglutide arms) completing the study.

The aforementioned sample size provides $\geq 90\%$ power to demonstrate superiority for the dulaglutide doses (4.5 mg, 3.0 mg, and 1.5 mg) to placebo with respect to HbA1c change from baseline to 18 weeks. This assumes a true glycemic effect difference of -1% HbA1c for each dulaglutide dose versus placebo, and a standard deviation (SD) of 1.2% with a 2-sided alpha of 0.05.

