6.1. General Considerations

Statistical analysis of this study will be the responsibility of Eli Lilly and Company or its designee. Any change to the data analysis methods described in the protocol will require an amendment ONLY if it changes a principal feature of the protocol. Any other change to the data analysis methods described in the protocol, and the justification for making the change, will be described in the statistical analysis plan (SAP) or the clinical study report (CSR). Additional exploratory analyses of the data may be conducted as deemed appropriate without further changes made to the protocol or SAP even after the datalock.

Countries with fewer than 10 randomized patients will be pooled for statistical analyses. Pooled country will be employed for all formal statistical model-based analyses as a block factor unless otherwise denoted.

Unless otherwise specified, all tests of treatment effects will be conducted at a 2-sided alpha level of 0.05, and confidence intervals (CIs) will be calculated at 95%, 2-sided. All tests of interactions between treatments and factors of interest will be conducted at a 2-sided alpha level of 0.10. No adjustments for multiplicity will be performed.

The baseline visit will be Visit 3. For all variables, including HbA1c, if baseline data are not available or are missing, the last nonmissing measurement taken prior to this visit will be used for the baseline measurement. The efficacy measure for the primary analysis is defined as the change from baseline in HbA1c to Week 18 (Visit 12).

For all statistical analyses, missing data will be treated as missing at random unless otherwise specified; therefore, no imputation is needed unless otherwise stated.

The treatment groups mentioned in this document are based on the randomized treatment groups: dulaglutide 4.5 mg, dulaglutide 3.0 mg, dulaglutide 1.5 mg, placebo. For the purposes of tables, figures, the treatment groups will be: Dula 4.5, Dula 3.0, Dula 1.5, and Placebo. For data listings, the treatment groups will be presented as Placebo, Dula 1.5, Dula 3.0/A1 representing dulaglutide 3.0 mg/algorithm 1, Dula 3.0/A2 representing dulaglutide 3.0 mg/algorithm 2, Dula 4.5/A1 representing dulaglutide 4.5 mg/algorithm 1, Dula 4.5/A2 representing dulaglutide 4.5 mg/algorithm 2.

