6.2. Adjustments for Covariates

The study is stratified by baseline HbA1c with country as a block factor; therefore, both stratification factors will be fitted in the corresponding statistical model as fixed effects for the non-HbA1c measurements unless otherwise stated. For HbA1c analysis, the strata of baseline HbA1c will be replaced with the covariate of baseline HbA1c. For other continuous variables other than some safety laboratory measures, a corresponding baseline measure will be added as a covariate.

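### Collinearity is not a sound reason to drop continuous baseline HbA1c from the baseline-HbA1c subgroup model; the precision lost is small

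*SAP*

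**What the plan says.** Protocol 10.3.6 and SAP 6.14 allow optional subgroup analyses of the primary endpoint. The Protocol's list of factors ends "baseline HbA1c (<8%, ≥8%), and BMI may be conducted for the primary endpoint of HbA1c". The SAP model is an MMRM with treatment, visit, subgroup and their interactions up to "treatment-by-visit-by-subgroup as fixed effects, and baseline as a covariate".

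There is one exception. SAP 6.14: "When analyzing baseline HbA1c as a subgroup, the baseline HbA1c will not be included as a covariate to avoid colinearity". Protocol 10.3.6 has the same rule: "the baseline HbA1c will not be included as a covariate to avoid colinearity". Neither document gives a collinearity diagnostic.

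Elsewhere the SAP resolves the overlap between the split and the continuous value the other way. SAP 6.2: "For HbA1c analysis, the strata of baseline HbA1c will be replaced with the covariate of baseline HbA1c". On testing, SAP 6.1 says: "All tests of interactions between treatments and factors of interest will be conducted at a 2-sided alpha level of 0.10".

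**The concern.** A two-level split of a variable is correlated with that variable but does not determine it, so a model with both terms can be estimated. The question is which coefficients pay for the correlation. If the interaction does not, the exception discards a prognostic covariate for no gain. It also makes the one subgroup model built on the endpoint's own baseline the only one not adjusted for it.

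The stakes are modest: some precision in an interaction test that has little power to begin with, adjustment for chance baseline differences within strata, and comparability with the other subgroup models.

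**Working it through.** **The plan's own figure.** The documents give no figure for the subgroup analysis. The nearest is the power statement in SAP 5.2: "This assumes a true glycemic effect difference of -1% HbA1c for each dulaglutide dose versus placebo", with SD 1.2%, two-sided alpha 0.05 and about 60 completers per arm. Then 1.0 / (1.2 × √(2/60)) = 4.56, and power = Φ(4.56 − 1.96) = 99.5%. The stated lower bound of 90% holds, and these inputs are carried forward.

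**Inputs.**
- From the documents: four arms of 60; SD 1.2%; interaction alpha 0.10; cut at 8%; entry criterion "have HbA1c of 7.0% to 10.0%, inclusive, as assessed by the central laboratory" (Protocol 6.1).
- Assumed, because the documents give neither: the baseline distribution (uniform on 7 to 10, or truncated normals, with and without extra variation between Visit 1 and Visit 3; resulting SD 0.57 to 0.90) and the slope of HbA1c change on baseline (−0.3 to −0.7).
- Base case: normal with mean 8.1 and SD 0.8, truncated to 7 to 10; slope −0.5. This gives baseline SD 0.661, 59.6% of patients at or above 8%, and pooled within-subgroup SD 0.396.
- Model: a Week 18 linear model with treatment, subgroup and their interaction, with and without continuous baseline, as an approximation to the MMRM.

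**Step 1: is there harmful collinearity?** In the base case r = 0.80, so VIF = 1/(1 − 0.80²) = 2.78. Across distributions r is 0.75 to 0.82 and VIF 2.3 to 3.0. The model is full rank (mean scaled condition number about 11 to 13, maximum 18).

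**Step 2: which terms pay?** Base case, simulated, 60 per arm:

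| Term | SE without baseline | SE with baseline | Ratio |
|---|---|---|---|
| Treatment-by-subgroup contrast | 0.439 | 0.433 | 0.987 |
| Subgroup effect, reference arm | 0.310 | 0.369 | 1.19 |
| Subgroup effect, averaged over arms | 0.155 | 0.256 | 1.65 |

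The variance factor due to design alone is about 1.003 for the interaction and 1.002 for the treatment difference within the <8% subgroup. Randomization makes baseline nearly unrelated to treatment within a stratum, so the cost of the correlation falls on the subgroup effect.

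**Step 3: what is lost by dropping baseline?** SE ratio ≈ √(residual variance without / residual variance with).
- Without: 1.44 − 0.5² × (0.661² − 0.396²) = 1.370.
- With: 1.44 − 0.5² × 0.661² = 1.331.
- √(1.370/1.331) = 1.015. The simulated ratio is 0.4388/0.4333 = 1.013, slightly lower because of the small design cost.

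Across the assumed slopes and distributions at SD 1.2 the inflation is 0.3% to 6.4% of the SE, equivalent to 0.7% to 13% more patients. If the true SD were 0.9 (also an assumption), it would be 0.6% to 15.5%.

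**Step 4: chance imbalance.** In the base case the baseline imbalance entering the interaction contrast has an SD of about 0.14 HbA1c points. At slope −0.5 a one-SD imbalance moves the unadjusted estimate by 0.5 × 0.14 = 0.07 points. This is the Step 3 loss seen another way, not a second benefit: √(0.4388² − 0.4333²) = 0.07.

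**Step 5: power.** For an assumed true interaction of 0.5 points at alpha 0.10:
- Without baseline: Φ(0.5/0.4388 − 1.645) + Φ(−0.5/0.4388 − 1.645) = 30.9%.
- With baseline, SE 0.4333: 31.4%.

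**The case against.** The strongest case for leaving the text alone has four parts.

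1. **The gain is trivial.** About 1% of an SE and half a percentage point of power in the base case. This stands. A reader might infer that the exception is why the interaction test is weak, or that removing it would restore power. It would do neither.
2. **The correlation is real.** A reader might infer that no collinearity arises at all. At r of about 0.8 that goes too far, since the subgroup main effect does become less precise. But SAP 6.14 names the treatment interaction as the object of the analysis, and that contrast is unharmed.
3. **LS means.** With a common covariate, subgroup LS means are by default evaluated at one overall baseline, which cannot represent both sides of the 8% cut. This is a fair reporting point. Evaluating them at each subgroup's own mean meets it without dropping the covariate.
4. **The analysis is valid, optional and already partly balanced.** Randomization is stratified at 8%, the split alone absorbs about 56% to 67% of baseline variance, and the SAP permits further analyses even after datalock. All of this stands. A reader might infer that omitting the covariate biases the interaction. It does not, because treatment is randomized. What remains is imbalance within strata.

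A reader might also suppose that HbA1c response depends more on baseline HbA1c than on any other listed factor. Neither document says so, and the point does not rely on it.

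**Conclusion.** The point holds as a minor one. The stated reason for the exception is wrong for the interaction, and the exception runs against the SAP's general preference for the continuous value in HbA1c analyses. The analysis as written remains unbiased and has no bearing on the primary result.

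The sizes rest on the assumed baseline distributions and slopes, and on a single-visit approximation to the MMRM. One uncertainty remains. The 7.0% to 10.0% limit applies at Visit 1 while baseline is Visit 3, and SAP 6.1 defines the strata by the Visit 1 value while SAP 6.2 refers to baseline. If the subgroup were formed from the Visit 1 value, its correlation with the Visit 3 covariate would be expected to be lower, which would weaken the collinearity argument further; this was not computed.

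**What to change.** Delete the exception sentence in SAP 6.14 and Protocol 10.3.6. Fit the baseline-HbA1c subgroup model with continuous baseline HbA1c as a covariate alongside the <8%/≥8% factor, as in the other subgroup models. State that any subgroup LS means are evaluated at each subgroup's own mean baseline.

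If the sponsor prefers not to change the main subgroup model, add the adjusted model as a sensitivity analysis and remove the collinearity rationale.

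The cost is one deleted sentence in each document and one line on LS means. No new data are needed. The downside is a less precise subgroup main effect, which is not of interest here.

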6.15. Important Protocol Deviations

Important protocol deviations will be listed for all randomized patients and summarized by treatment group. All important deviations related to study inclusion or exclusion criteria, conduct of the trial, patient managements or patient assessment will be described. The important protocol deviations will be prospectively defined in the study-specific monitoring requirements. Some of the protocol deviations that may not be prospectively identified may later be considered important by the Lilly study team, in which case will be also reported. The important protocol deviations will be captured from the clinical trial database as well as an excel file managed by the study clinical trial manager (CTM). The excel file generated by the CTM will be converted in a domain of the study data tabulation model (STDM) as a source in addition to other necessary SDTM domains to define the PP population. The rationale for choosing certain important protocol deviations as exclusionary from the PP population will be based on their potential effect on the primary efficacy measures. The decision and rationale for not reporting certain protocol deviations as important ones will be documented in the eTMF. The following protocol conditions will result in exclusion from the PP population:

- informed consent was never obtained
- patients were randomized but the informed consent date is missing.
- age <18 years old at randomization
- patients have known type 1 diabetes
- patients who had any hematologic condition that may have interfered with HbA1c measurement (eg, hemolytic anemias, sickle-cell disease)
- excluded medicine use prior to safety follow-up
 - weight loss agents,
 - prohibited glucose-lowering agents (>14 days of use during the treatment period or any time during the screening/lead-in period of sulfonylureas, thiazolidinediones, alpha-glucosidase inhibitors, SGLT2 inhibitors, meglitinides, other GLP receptor agonists or DPP4 inhibitors, etc.)
 - >14 days use of systemic glucocorticoid
- patients have an HbA1c <7% or >10% at Visit 1.
- patients have a missing HbA1c at baseline (both Visit 1 and Visit 3) or at 18 weeks (Visit 12).
- patients do not have an overall compliance with study drug of at least 75% up to 18 weeks.

A complete list and summary report of important protocol deviations will be generated.

6.16. Interim Analyses and Assessment Committee

At least three safety interim analyses and one efficacy/safety interim analysis will be conducted according to the specifications included in the protocol. The purpose of the safety analyses will be to monitor the safety and tolerability of the 2 investigational dulaglutide doses. The interim efficacy/safety analysis will be conducted for internal clinical development planning purposes to enable preliminary dose-selection for Phase 3 planning. The study will not be stopped based on the efficacy results at this interim analysis.

6.16.1. Assessment Committee

The interim analyses will be conducted under the auspices of an Assessment Committee (AC). The AC is authorized to review unblinded interim analyses. Before any interim analysis is performed, an AC will be established to control the dissemination of the findings. Lilly representatives having direct contact with the investigative sites will not be part of the AC unless they stop contact with the sites from the time of their inclusion into the study AC. Statistical Analysis Center (SAC) will be authorized to evaluate unblinded interim analyses and prepare the reports for the AC to review. Study sites may receive information about interim results ONLY if these results may have an impact on the safety of patients in this trial.

The AC proceedings will be described in an AC charter. Any change to the proceedings will be included in the AC charter and will not require a protocol or SAP amendment. The AC Charter describes the precise plan of the unblinded safety monitoring and interim statistical analyses.

6.16.2. Interim Analyses

6.16.2.1. Timing of the Interim Analysis

The first safety only interim analysis will occur after approximately 15 patients have completed 8 weeks of treatment. The AC will continue to evaluate patient safety and tolerability when approximately 30 patients and 60 patients complete 8 weeks of treatment.

The efficacy/safety interim analysis will be conducted after approximately 120 patients have completed the 18-week treatment period.

6.16.2.2. Evaluation Criteria

For safety only interim analyses, the totality of the safety data on AEs, SAEs, TEAEs, and AESIs, disposition, discontinuation due to AEs, ECG, vital signs, ADA, GI AEs, cardiovascular events, and safety laboratory analytes will be evaluated. The analysis for each mentioned parameter will be analyzed in the same way as defined in this SAP.

For efficacy/safety analysis, the AC will base their decision on the following criteria in addition to the safety parameters listed in the preceding paragraph:

HbA1c Criterion:

At least 80% probability that at least one dose of dulaglutide 3.0 or dulaglutide 4.5 mg reduces HbA1c by at least 0.2% compared to dulaglutide 1.5 mg at Week 18, that is,

$\Pr(\Delta_{\text{dula3.0 or dula4.5}} - \Delta_{\text{dula1.5}} < -0.2\%) \geq 80\%$]. The other thresholds of -0.15% and -0.3% will be also be evaluated. The probability will be at least 55% at the end of the study.

Other efficacy endpoint at week 18: change from baseline in body weight, will also be assessed relative to 1.5 mg as, $\Pr(\Delta_{\text{dula3.0 or dula4.5}} - \Delta_{\text{dula1.5}} < \text{threshold of } -1 \text{ and } -2 \text{ kg.}$

Safety Parameters:

Heart rate from ECG, pulse rate from vital signs using change from baseline to be assessed relative to placebo as, $\Pr(\Delta_{\text{dula3.0 or dula4.5}} - \Delta_{\text{placebo}} < \text{threshold of } 3, 5, 7, 10 \text{ bpm.}$

MMRM analysis results will be reported for change from baseline in HbA1c, body weight, selected ECG, vital signs, and pancreatic enzymes, too.

PK/PD exposure-response results will be generated based on a separate PK/PD analysis plan by PK/PD group.

6.17. Planned Exploratory Analyses

Some of the planned exploratory analyses are described in Section 6.1. The remaining exploratory exploratory analyses are described in this Section.

The analysis of patients reaching HbA1c target $\leq 6.5\%$ will use the same model as that for HbA1c target $< 7.0\%$ described in Section 6.11.3.

Longitudinal continuous variables such as fasting glucagon will be analyzed using MMRM described in Section 6.1. If the normality assumption is violated, appropriate data transformation is needed prior to analysis.

Non-longitudinal continuous variables such as 6-point SMPG, c-peptide, fasting insulin, HOMA2-IR, and HOMA2-%B will be analyzed using LOCF by fitting a linear model with pooled country, treatment, baseline HbA1c strata as fixed effects and the corresponding baseline value as a covariate. A data transformation may be applied if data are not normally distributed.

The 6-point SMPG consists of measurements before and 2 hours after each of 3 main meals within the same day. Each of the time point of the 6-point SMPG will be analyzed separated.

6.18. Annual Report Analyses

The following reports are needed for the Development Safety Update Report (DSUR): (1) Estimated cumulative subject exposure, (2) Cumulative exposure to investigational drug, by demographic characteristics for ongoing unblinded clinical trials and completed clinical trials, (3) Exposure information for ongoing clinical trials and clinical trials that completed during the reporting period, (4) Listing of subjects who died during the DSUR period, (5) Discontinuations from the study due to adverse event, (6) Discontinuations from the study treatment due to adverse event during the DSUR Period.

6.19. Clinical Trial Registry Analyses

Additional analyses will be performed for the purpose of fulfilling the Clinical Trial Registry (CTR) requirements.

Analyses provided for the CTR requirements include the following:

Summary of adverse events, provided as a dataset which will be converted to an XML file. Both SAE and 'Other' AE are summarized: by treatment group, by MedDRA preferred term.

- An adverse event is considered 'Serious' whether it is a treatment emergent adverse event (TEAE).
- An adverse event is considered in the 'Other' category if it is a TEAE but not serious. For each Serious AE and 'Other' AE, for each term and treatment group, the following are provided:
 - the number of participants at risk of an event
 - the number of participants who experienced each event term
 - the number of events experienced
- Consistent with www.ClinicalTrials.gov requirements, 'Other' AEs that occur in fewer than 5% of patients/subjects in every treatment group may not be included if a 5% threshold is chosen (5% is the minimum threshold).
- AE reporting is consistent with other document disclosures for example, the CSR, manuscripts, and so forth.

7. Unblinding Plan

The purpose of the unblinding plan is to detail the procedures that are in place to minimize bias while preparing for or conducting any summary or analysis of the data for AC reports, data reviews, dose selection (interim efficacy/safety only), and developing/refining exposure analyses. Additionally, this plan identifies personnel who will be unblinded during the study, including unblinding for the AC safety only analyses, and safety/efficacy interim analyses in support of the AC meetings.

The access to subject treatment assignments will not be provided to the following personnel until datalock is authorized for the planned final analysis at the completion of the blinded study:

- investigator and site personnel
- Lilly personnel with direct site contact
- Lilly personnel responsible for data entry and data validation
- Lilly study team not in the AC and/or SAC

After datalock, the study team will be unblinded to the study data to prepare for the analyses for CSR. Investigators can be provided treatment assignments for their subjects when unblinding has occurred and the information will not impact scientific integrity or introduce bias.

